## **9.7.3. Safety Studies**

### **9.7.3.1. Characteristics of study cohorts**

Characteristics of the study cohorts will be described for bisphosphonates new users and strontium ranelate new users. These will be all contra-indications, precautionary conditions and co-variables. Chi-square tests will be conducted to test differences in distributions.

### **9.7.3.2. Absolute rates of safety endpoints**

The crude and age and sex specific incidence rates of each of the safety endpoints events will be estimated separately in new SR and oral bisphosphonate users assuming a Poisson distribution. Incidence rates will be stratified by period (up till May/2013 and from June/2013 onwards) and by number of newly defined (contra) indications at cohort entry. Graphs will be created that show the incidence rates of endpoints during use of study drugs and after use of study drugs.

### 9.7.3.3. Relative risks

Using a matched case control approach we will use conditional logistic regression to estimate the association with the occurrence of endpoints and between current use of SR and 1) past use of study drugs; 2) current use of bisphosphonates. Control for confounding will be based on the change in estimate method as proposed by Greenland *et al* (1993). All analyses will be stratified by period. We will primarily consider factors measured at baseline, and only for those at index date for which we are sure they cannot be an intermediate between drug exposure and outcome.

### 9.7.4. Pooling

All estimates will be calculated by databases and pooled according to a meta-analysis approach (random or fixed effects model). In addition, to optimize power, we will conduct a mega-pooled analysis, that will estimate the effects putting all individual level data together (fixed and random effects will be checked).

### 9.7.5. Sensitivity analyses

Sensitivity analyses will be conducted based on the gap period (persistence assessments) and the risk window for exposure.

In addition, sensitivity analyses excluding participating countries where legal restrictions are in place for the prescription of SR in primary care (i.e. Spain) will be carried out for both the RMM effectiveness and safety studies, and reported accordingly.

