## 6. MILESTONES

Milestone	Planned date
Protocol submission to EMA	by 30 June 2014
Protocol approval by EMA	March 2015 *
Contract signature for study roll-out phase	April 2015*
Registration in the EU PAS register	April 2015*
Start of data collection	April 2015*
Statistical Analysis Plan	May 2015
End of data collection	End of June 2015
PSUR Update 1	October 2015
Start of data collection (second wave)	April 2016
End of data collection (second wave)	End of June 2016
PSUR Update 2	October 2016
Start of data collection (third wave)	April 2017
End of data collection (third wave)	End of June 2017
PSUR Update 3	October 2017
Final report of study results	End of November 2017

*\*Delay will impact the subsequent dates*

Milestones have been planned to maximise the efficiency and availability of data retrieval from the different data sources. A summary of such information is provided here:

Data source (Country)	Periodicity of updates	Time of the year when updates are released	Data availability for each update
SIDIAP (Spain)	Yearly	April-May	End (December 31 st ) of previous calendar year
IPCI (NL)	Yearly (twice is possible)	April-May	Variable as GPs provide not all at same time
THIN (UK)	Three times per year	Irregular	Variable as GPs provide not all at same time
HSD (Italy)	Every 6 months	June and December	End of previous calendar year (in June); up to June in December.
AUH (Denmark)	Yearly	May	December 31st the previous year

Both national regulations and prescribing practices have changed throughout the participating databases in recent months. As a consequence, in Italy, where GPs in primary care are not allowed anymore to initiate or renew strontium ranelate treatment since December 2013, the number of incident strontium ranelate users in the assessment period is expected to be null or very low. This point will be assessed for the first PSUR update (October 2015) as part of the analyses of the utilization patterns at population level (see [section 9.7.2.1](#)).

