## Safety

1. To estimate the incidence rates of cardiac and thromboembolic events in SR users with and without contra-indications prior and from June 2013.
2. To compare the risk of cardiac and thromboembolic events between new users of SR and new users of oral bisphosphonates without contra-indications, both before and from June 2013.

All of these research objectives will be addressed for the overall eligible population but also after stratification by country, gender, period (three analysis periods (reference, transitional, and assessment) for the assessment of RMM effectiveness, and two periods (before and from June 2013) for the safety studies), month and age, and presence/absence of contra-indications, when applicable/relevant.

In addition, sensitivity analyses excluding participating countries where legal restrictions are in place for the prescription of SR in primary care (i.e. Spain) will be carried out for both the RMM effectiveness and safety studies, and reported accordingly.

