#### NEW INDICATIONS OF USE

Regarding the new restrictions, some of these criteria are not directly captured in the databases. Thus, operational definitions are proposed using some proxies which could lead to some misclassification or underestimation of the new restrictions. Therefore, some validation or refinement steps based on data availability and quality are required and will be further discussed with each of the academic partners before data extraction; for instance through feasibility assessed on a random sample.

- *A physician with experience in the treatment of osteoporosis.* The operational definition for this in our data sources will be:
  - Therapy initiation in secondary care settings (where available: Aarhus Database)OR
  - Therapy initiation in primary care by a physician with a “high number” of patients diagnosed with osteoporosis or on anti-osteoporosis treatment under his/her care. As both national regulations and prescribing practices have changed throughout the participating databases in recent months (e.g. general practitioners are not allowed to either initiate or prescribe repeat prescriptions of SR in Italy, different to Spain, where GPs cannot initiate but can issue repeat prescriptions of the drug), the definition of “high number” of patients with a diagnosis or treatment for osteoporosis will be based on national figures: a GP will be classified as “experienced” (with a high number of osteoporotic patients) if the number of patients with a diagnosis or treatment for osteoporosis registered with him/her is above a discriminant threshold; for instance, in the top quartile (percentile 75 or above) in the same country/data source.
- *Initiation of SR therapy not in first line,* will be operationalized as:
  - Previous use of other anti-osteoporosis drugs at any time before SR therapyOR
  - History of any formal contra-indications or precautions for the use of oral bisphosphonates (according to SmPC for alendronic, risedronic and ibandronic acid) not recognised as contra-indications or precautions for the use of SR [Appendix 14.3] at any time before SR therapy.

- Use of SR for the treatment of severe osteoporosis, will be operationalized as:
  - History of a previous osteoporotic fracture [Appendix 14.3.2] (at any time before SR therapy initiation).
- OR

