**Table (9.4) 1 - Overview of contributing databases**

Country	Netherlands	United Kingdom	Denmark	Italy	Spain
Name of the database	IPCI	THIN	Aarhus	HSD- Thales	SIDIAP
Type of database	MR	MR	ADM	MR	MR
# patients, millions	1.2	3.5	1.8	1.5	5.1
Age categories	All	All	All	>15 years	>15 years
Date in	Yes	Yes	Yes	Yes	Yes
Date out	Yes	Yes	Yes	Yes	Yes
Date death	Yes	Yes	Yes	Yes	Yes
Prescriptions					
Outpatient Rx	Yes (specialist incomplete)	Yes (specialist incomplete)	Yes	Yes (specialist incomplete)	Yes (specialist incomplete)
Coding of drugs	ATC	BNF/Multilex	ATC	ATC	ATC
Dosing regimen	Yes	Yes	No	Yes (incomplete)	Yes
Outcomes					
Hospitalizations	Yes	Yes	Yes	Yes	Yes
Outpatient diagnoses	Yes	Yes	Yes	Yes	Yes
Coding of disease	ICPC	READ	ICD-10	ICD-9 CM	ICD-10
Cause of death	Yes (from text)	If linked to death registry	Yes	No	No

*ADM = administrative; ATC = Anatomical Therapeutic Chemical; BNF = British National Formulary; ICPC = International Classification of Primary Care; MR = Medical Records*

All of the chosen databases comply with European Union (EU) guidelines on the use of medical data for medical research and have been validated for pharmaco-epidemiological research (Cazzola, 2011; Vlug, 1999).

The databases will be THIN (UK), HSD (Italy), IPCI (NL), the Aarhus University Database (DK) and SIDIAP (Spain). Table (9.4) 1 provides an overview of key elements of these databases. The total number of persons in the source population will be around 12 million as of 2012.

HSD (Italy), IPCI (Netherlands), SIDIAP (Spain) and THIN (UK) are listed under the ENCePP resources database: ([www.encepp.eu/encepp/resourcesDatabase.jsp](http://www.encepp.eu/encepp/resourcesDatabase.jsp)).

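### The sensitivity analysis that removes countries with legal prescribing restrictions names only Spain, although the protocol describes a stricter restriction in Italy

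*Protocol*

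**What the plan says.** The same exclusion rule stands in four places in the protocol: twice in the abstract (data analysis and safety), at the end of section 8, and in section 9.7.5. Section 9.7.5 words it as "sensitivity analyses excluding participating countries where legal restrictions are in place for the prescription of SR in primary care (i.e. Spain"). The gloss reads as a complete list with Spain as its only member.

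Two other sections describe the Italian position. Section 6 refers to the situation "in Italy, where GPs in primary care are not allowed anymore to initiate or renew strontium ranelate treatment since December 2013". It expects incident SR users there to be absent or nearly so in the assessment period. Section 9.3.2, under the new indications of use, says that "general practitioners are not allowed to either initiate or prescribe repeat prescriptions of SR in Italy", and contrasts this with Spain, "where GPs cannot initiate but can issue repeat prescriptions of the drug".

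The Italian source, HSD, is built from GP records (section 9.4.2). Table (9.4) 1 gives its outpatient prescriptions as "Yes (specialist incomplete"). Section 6 plans to look at Italian use in the population-level utilization analyses for the first PSUR update. Nothing carries that into the sensitivity analysis or the safety study.

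**The concern.** The sensitivity analysis exists to show whether the findings survive once national restrictions on primary-care prescribing are taken out. By the protocol's own account, Italy has such a restriction, and it is tighter than the Spanish one because repeats are barred too. A pooled result that drops Spain and keeps Italy would be presented as free of legal restrictions when it is not.

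Two conclusions are affected. In the RMM study, a change in Italian use caused by the ban could be credited to the risk minimization measures. In the safety study, Italian patients who continue SR under a specialist may have no further prescriptions in the GP record and so be classed as no longer exposed. The protocol's discussion of exposure error in section 9.9 covers prescriptions that are written but not taken up. That is error in the other direction.

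**Working it through.** **1. Does Italy meet the criterion?** The criterion is a legal restriction on prescribing SR in primary care.

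| | GP may start SR | GP may repeat SR | Named in the exclusion |
|---|---|---|---|
| Spain (section 9.3.2) | no | yes | yes |
| Italy (sections 6 and 9.3.2) | no | no | no |

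Italy meets it more fully than Spain does.

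**2. Where does the ban fall in time?** The transitional period, used as the lag in the interrupted time series (ITS, section 9.7.2.2), is June 2013 to March 2014, 10 months. The ban starts in December 2013 and so covers the last 4 of them. By April 2014, when the assessment period opens, both the RMM and the ban are in force. A before-and-after contrast in the Italian series cannot separate the two.

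**3. How many users are involved?** Inputs are the 2012 counts in Table (9.5) 1. The five incident rows reproduce the printed total: 1,209 + 4,008 + 514 + 46 + 42 = 5,819. So do the prevalent rows: 10,129 + 14,502 + 2,563 + 464 + 106 = 27,764.

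| | Incident | Prevalent |
|---|---|---|
| Without Spain | 5,819 − 4,008 = 1,811 | 27,764 − 14,502 = 13,262 |
| Italian share of that | 1,209 / 1,811 = 66.8% | 10,129 / 13,262 = 76.4% |
| Without both | 1,811 − 1,209 = 602 | 13,262 − 10,129 = 3,133 |
| As share of all users | 602 / 5,819 = 10.3% | 3,133 / 27,764 = 11.3% |

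The prevalent counts by sex do not add up to the printed row totals for Italy (613 + 9,616 = 10,229, not 10,129) or Denmark (42 + 412 = 454, not 464). With the sex sums the Italian prevalent share is 10,229 / (10,229 + 2,563 + 454 + 106) = 76.6%, so nothing changes.

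**4. Do these shares hold after the ban?** No. Let r be the fraction of 2012 Italian use that remains, with the other databases unchanged (an assumption). The Italian share without Spain is then 1,209r / (602 + 1,209r) for incident users and 10,129r / (3,133 + 10,129r) for prevalent users.

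| r | Incident | Prevalent |
|---|---|---|
| 0 | 0% | 0% |
| 0.05 | 9% | 14% |
| 0.10 | 17% | 24% |
| 0.25 | 33% | 45% |
| 0.50 | 50% | 62% |
| 1 | 67% | 76% |

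Section 6 points to the top of the table for incident users. Italy is thus a large part of the pooled data before the ban and probably a small part afterwards.

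**5. What happens to exposure in the safety study?** Section 9.3.3 classes a patient as current up to 30 days after the last prescription ends, recent from 30 to 180 days, and past beyond 180 days. Take a patient whose last GP prescription runs out on 30 November 2013 and whose continuing specialist prescriptions are not recorded. That patient is recent until about 29 May 2014 (180 days) and past from then on. Section 9.7.3.3 has two contrasts:

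- Current SR against past use of study drugs: events that occur on SR could be counted in the reference group. This would pull a raised odds ratio towards 1.
- Current SR against current bisphosphonate: the patient does not move into the reference group. The contrast mainly loses SR-exposed time and cases.

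Periods are assigned by date of cohort entry, and follow-up runs to the end of enrolment or of data capture (section 9.2.6.2). Italian patients who entered before June 2013 can therefore carry time after the ban into the first-period stratum as well.

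**The case against.** The strongest reply is that this is an incomplete parenthesis in a secondary analysis. Each data source has its own time series and serves as its own control, estimates are made by database before pooling (section 9.7.4), and results are stratified by country. A reader will be able to see Italy separately. This stands and softens the point, but it does not correct the pooled result without Spain.

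Other parts of the reply also stand:

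- The contraindication and indication outcomes in the time series are proportions among SR users, so falling counts do not by themselves look like an RMM effect.
- Table (9.4) 1 calls specialist prescriptions incomplete, not absent, and gives the same label to the Dutch, UK and Spanish databases. The protocol does not say how many Italian patients continued under specialists.
- Section 9.5.2 expects at least 30,000 of 31,500 to 33,000 SR initiators to enter in 2004-2012 and assumes 2 years of average follow-up. Much of the safety data therefore precedes the ban.
- Section 6 already plans a check of Italian utilization. That check is framed around incident users and is not tied to the sensitivity analysis, although repeats are barred too.

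**Conclusion.** The contradiction is established: the exclusion rule as written keeps a country that meets its own criterion, and the pooled analysis without Spain cannot be read as free of national restrictions. It rests only on the protocol's own description of the Italian and Spanish rules. The size, 67% of incident and 76% of prevalent users without Spain, rests on 2012 counts. Under-capture of Italian SR exposure after December 2013 is a risk inferred from the nature of the database.

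A reader might infer four stronger things that the documents do not support:

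- That the analysis without Spain would be 67-76% Italian throughout. The shares predate the ban, are not meta-analysis weights, and should fall afterwards.
- That Italian exposure is mismeasured as a matter of fact. Neither its occurrence nor its extent is given.
- That the odds ratio is pulled towards 1 in general. This applies to the past-use contrast only, and only beyond 180 days.
- That 602 and 3,133 are the restriction-free evidence base. They are one-year counts, and section 9.3.2 gives Italy and Spain as examples of wider regulatory change. It does not show the other three countries to be unrestricted.

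**What to change.** Reconcile the exclusion rule with sections 6 and 9.3.2. If their description of Italy is correct, change the gloss to '(i.e. Spain and Italy)' in both places in the abstract, in section 8 and in section 9.7.5. Report results without Spain, without Italy and without both, giving the number of users in each.

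For the safety study, prespecify a sensitivity analysis that censors HSD at 30 November 2013, and leave the main analysis as it is. For the ITS, flag HSD months from December 2013 when results are interpreted. Declaring them not assessable in advance would pre-empt the check planned in section 6.

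The cost is wording and a few extra runs. The analysis without both countries will be small and imprecise, which readers should see. The censored run discards some valid Italian bisphosphonate follow-up and events, which is why it belongs in a sensitivity analysis.

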## 9.8. Quality control

This study was designed and shall be implemented and reported in accordance with the Guidelines for Good Pharmacoepidemiology Practices (GPP) of the International Society for Pharmacoepidemiology (ISPE, 2008), the STROBE (Strengthening the Reporting of Observational Studies in Epidemiology) guidelines (von Elm, 2008), and with the ethical principles laid down in the Declaration of Helsinki.

This study is fulfilling the criteria of a ‘European Network of Centres for Pharmacoepidemiology and Pharmacovigilance (ENCePP) study’ and follows the ‘ENCePP Code of Conduct’ (2014).

All programs will be programmed according to agreed coding standards and will be validated by double programming or source code review with second programmer involvement.

Only validated software (SAS version 9.2, SAS Institute Inc., Cary, NC) will be used for statistical analysis.

## 9.9. Limitations of the research methods

This study is non-interventional and as such has several important limitations.

### Selection bias

Since the study is based on electronic health care records and does not require active consent of participants, lack of participation that may lead to selection bias is not an issue in this study.

## Information bias

Information bias may occur to not measuring correctly exposure, outcomes or co-variables.

Regarding exposure, most databases that participate in the study capture prescriptions rather than dispensings. Misclassification of exposure may occur due to lack of ‘picking up’ the prescribed medication and non-compliance. This may overestimate utilization of SR/BP and lead to non-differential misclassification of the comparative studies. Misspecification of the risk window may lead to information bias. The effect of a potential misspecification will be addressed in sensitivity analyses

Lack of recording of certain co-variables (e.g. history of fractures rather than BMD) may lead to misclassification and underestimation of the contra-indications and new indications. Similarly, lack of recording of safety events may lead to misclassification of the safety endpoints. However, previous work has shown very high validity of the coding of myocardial infarction, with positive predictive values ranging from 75% to 100% within EU-ADR Alliance partners (Coloma, 2013). DVT and VTE were only validated in some databases before and will therefore need validation in each of the data sources. Cardiovascular death may be misclassified if no autopsy is done. Validation studies will be conducted in databases where this information is not yet available (See Section 9.3.1).

## Confounding

Due to the observational design chosen, causality in the observed associations will not be established. Instead, associations between drug use and risks will be assessed. As confounding by indication (with SR patients most likely to suffer more severe osteoporosis) will likely produce differences between SR and bisphosphonate users, especially after the different DHPCs, we will use several methods to deal with between-person confounding:

1. Restriction: comparative studies will be conducted only in persons without contra-indications to restrict the population to those that would be prescribed SR according to the new label.
2. Matching: for the comparative studies we will match cases to controls on age, sex, date, country.
3. Adjustments: we will adjust for all co-variables that are associated with a 10% change in the primary risk estimate.

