### **New indications/prescribing conditions**

Experienced prescriber; treatment not in first line; severe osteoporosis

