### 7.2. Regulatory action

In the frame of 13th PSUR assessment, data submitted raised concern regarding cardiovascular safety beyond the already recognized risk for venous thromboembolism. Analysis of pooled data from randomized studies in around 7,500 post-menopausal women with osteoporosis showed an increased risk of myocardial infarction with Protelos/Osseor as compared with placebo (1.7% versus 1.1 %), with a relative risk of 1.6 (95% CI, 1.07 to 2.38), and an increased risk of venous thrombotic and embolic events — 1.9% versus 1.3 % with a relative risk of 1.5 (95% CI, 1.04 to 2.19).

As a result of this assessment, an increased risk for serious cardiac disorders, including myocardial infarction has been identified and risk minimization measures specifically targeting this identified risk were recommended by the CHMP. These risk minimization measures included a restriction of the target population by excluding patients with established, current or past history of ischaemic heart disease, peripheral arterial disease and/or cerebrovascular disease and/or uncontrolled hypertension, and restricting the indication to severe osteoporosis in postmenopausal women at high risk for fracture to reduce the risk of vertebral and hip fractures and the treatment of severe osteoporosis in adult men at increased risk of fracture. Patients with significant risk factors for cardiovascular events (e.g. hypertension, hyperlipidaemia, diabetes mellitus and smoking) should only be treated with strontium ranelate after careful consideration. In addition, strontium ranelate therapy should only be initiated by a physician with experience in the treatment of osteoporosis. These changes were disseminated in the form of a DHPC in May 2013.

In view of this newly identified risk of serious cardiac disorders, an overall benefit/risk review under Article 20 of regulation (EC) No 726/2004 started in May 2013 and was finalized on 20 February 2014 ([EMA/112925/2014, 2014](#)). This led to a restriction of the indication to patients (postmenopausal women and men) with severe osteoporosis at high risk of fracture for whom treatment with other medicinal products approved for the treatment of osteoporosis is not possible due to, for example, contraindications or intolerance. As part of RMM, a new DHPC was disseminated in March 2014.

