### 9.2.5.3. Comparative safety study

Patients with any of the newly defined contra-indications will be excluded:

1. Established, current or past history of ischemic heart disease (IHD),
2. Peripheral arterial disease (PAD),
3. Cerebrovascular disease (CVD),
4. Uncontrolled hypertension, defined by MAH using an operational definition as follows: a patient will be defined as 'uncontrolled hypertension' if the 3 following conditions apply:
  - a. There is a previous diagnosis of hypertension coded in electronic medical records.
  - b. There is documented use of any anti-hypertensive therapy (either at that time or in the previous year before SR/BP initiation).
  - c. There are at least two readings of Systolic Blood Pressure  $\geq 150$  or Diastolic Blood Pressure  $\geq 95$  mmHg recorded in the 3 months prior to SR/BP initiation.

Also, eligible patients with a diagnosis of Paget's disease of bones will be excluded. And for the outcome VTE we will exclude patients with a previous VTE.

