### 9.5.1. RMM effectiveness study

[figure not shown]
Based on published studies, the combined prevalence of MI, CVD and PAD before the DHPC published in May 2013 is assumed to be of 19.2% in female and 29.5% in male new users of SR (Abrahamsen, 2014).

A total of **320** male users of SR will suffice to estimate with a 95% confidence and an absolute precision of  $\pm 0.05$ , an unchanged prevalence of MI/CVD/PAD of 29.5%. Similarly, **239** female SR users would suffice to estimate with a 95% confidence and an absolute precision of  $\pm 0.05$ , an unchanged prevalence of MI/CVD/PAD of 19.2%.

Regarding the prevalence of new indication/restrictions of use (severe osteoporosis, and second line therapy), recent data suggest that the prevalence of these would range from 13.0% (Svanstrom, 2014) to 53.1% (Abrahamsen, 2014) for previous fragility fracture (severe osteoporosis), and from 40.4% (Svanstrom, 2014) to 47.9% (Abrahamsen, 2014) for the use of SR as a second line anti-osteoporosis treatment. Given this, 383 users of SR would suffice to estimate (with 95% confidence and 5% precision) an unchanged prevalence of 53.1% (most conservative scenario) for both indications. Lower numbers would be needed if this prevalence either increases or decreases (See Figure (9.5.1) 1).

A number of scenarios with different possible prevalence rates of MI/CVD/PAD, previous osteoporotic fracture, and use as a second line anti-osteoporosis therapy amongst SR users in subsequent years in the period before the publication of the DHPC in May 2013 (*reference*) and after the publication of the second DHPC from April 2014 onwards (*assessment* period) are presented in Figure (9.5.1) 1.

**Figure (9.5.1) 1 - Number of SR users required to estimate the prevalence of contraindications or new indication/restrictions with a 5% absolute precision**

[figure not shown]
For the interrupted time series analyses (see details below), sample size calculations are related to the estimation of the number of observations or time points at which data will be collected. According to the quality criteria of Ramsey et al, at least 10 pre- and 10 post-intervention data points would be needed to reach at least 80% power to detect a change (if the autocorrelation is  $>0.4$ ) (Ramsay, 2003). Our outcomes will be estimated at monthly intervals to ensure that  $>10$  data points are available for both the pre-defined *reference* and *assessment* analysis periods.

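### Excluding contraindications does not limit the comparison to patients who would get strontium ranelate under the new label, and it leaves osteoporosis severity to optional covariates

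*Protocol*

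**What the plan says.** Section 9.9 (Confounding) expects strontium ranelate (SR) patients to have more severe osteoporosis than bisphosphonate (BP) patients, especially after the two safety letters (DHPCs). It lists three defences: restriction, matching and adjustment. Under restriction, the comparative studies are "conducted only in persons without contra-indications to restrict the population to those that would be prescribed SR according to the new label".

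Section 7.2 describes that label. The first change, sent out in May 2013, included "restricting the indication to severe osteoporosis in postmenopausal women at high risk for fracture", with a parallel severe-osteoporosis condition for men. The 2014 review narrowed it to patients "with severe osteoporosis at high risk of fracture for whom treatment with other medicinal products approved for the treatment of osteoporosis is not possible". The Abstract lists the new prescribing conditions as "Experienced prescriber; treatment not in first line; severe osteoporosis".

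Section 9.3.2 turns these conditions into data definitions:
- Severe osteoporosis is a previous osteoporotic fracture, or a 5-year fracture risk of at least 10% on the Garvan tool.
- Not first line is another osteoporosis drug at any earlier time, or "History of any formal contra-indications or precautions for the use of oral bisphosphonates" that do not also apply to SR.

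The safety cohort (9.2.4) takes new SR or oral BP users aged 50 or over with one year of enrolment. For the comparison, 9.2.5.3 adds "Patients with any of the newly defined contra-indications will be excluded" and removes Paget's disease. Prior venous thromboembolism (VTE) is removed for the VTE outcome only, although the Abstract and 9.3.2 both list it as a contraindication.

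**The concern.** Section 9.9 names severity as the source of confounding and puts restriction first among its defences. The restriction acts on cardiovascular history and blood pressure. It does not act on severity or line of therapy, and neither does matching on age, sex, date and country. Only adjustment is left, and under the change-in-estimate rule it may drop the severity variables.

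Two things are at stake. A regulator who reads section 9.9 could take the odds ratio as the risk in label-eligible patients, which the design does not deliver. And the reader is told that a defence against confounding by severity is in place when it is not.

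**Working it through.** **1. What the label asks and what the cohort imposes**

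| Condition on the protocol's account | Imposed on the comparative cohort? |
|---|---|
| No ischaemic heart, peripheral arterial or cerebrovascular disease, no uncontrolled hypertension | Yes (9.2.5.3) |
| No prior VTE (Abstract, 9.3.2) | For the VTE outcome only |
| Severe osteoporosis (from 2013) | No |
| Other osteoporosis drugs not possible (from 2014) | No |

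**2. What is left for severity.** Section 9.3.4 lists fracture history, expressly as a severity proxy, and osteoporosis drugs in the prior year (9.3.2 looks back any time). Both are candidates under the change-in-estimate method (9.7.3.3), with the 10% threshold given in 9.9. Garvan risk and BP contraindications or precautions are defined elsewhere in the protocol but are not on the covariate list.

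**3. The plan's own figure.** Section 9.5.2 expects at least 25,128 SR users after exclusions: 31,500 × [1 − (0.10 × 0.295 + 0.90 × 0.192)] = 31,500 × 0.7977 = 25,128. This reproduces, and it reflects contraindications only.

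**4. Share of SR users with both a prior fracture (f) and second-line use (s).** Section 9.5.1 gives both shares from each of two Danish register studies. The joint share lies between max(0, f + s − 1) and min(f, s), and equals f × s under independence.

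| Source | f | s | Lower bound | Independent | Upper bound |
|---|---|---|---|---|---|
| SR starters 2005–2007 | 53.1% | 47.9% | 1.0% | 25.4% | 47.9% |
| SR starters 2005–2011, women | 13.0% | 40.4% | 0% | 5.3% | 13.0% |

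Applied to 25,128 users, the upper bounds are 12,036 and 3,267.

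**5. How firm is this over the whole study period?** Section 9.5.2 expects 30,000 SR starters in 2004–2012 and 500 to 1,000 a year in 2013–2015. Suppose all the later starters were on label and the earlier ones sat at the 47.9% ceiling. The on-label share would be (1,500 + 30,000 × 0.479) / 31,500 = 50.4%, or (3,000 + 30,000 × 0.479) / 33,000 = 52.6%.

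**6. The BP group.** It is 125,640 of 150,768 planned patients, or 83.3%. It is 80.0% if the stated 20% SR use is applied directly, giving 4 × 25,128 = 100,512 BP users. Read literally, the 2014 condition excludes nearly all of them, since they received another approved drug. On the 9.3.2 proxies the protocol gives no figure.

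**7. Cost of a severity-restricted subset (illustration).** Assume the fracture shares of 9.5.1 hold in both groups, with the protocol's 0.19 per 100 person-years and 2 years of follow-up:
- 150,768 × 0.130 × 2 × 0.0019 = 74 myocardial infarction cases
- 150,768 × 0.531 × 2 × 0.0019 = 304 cases

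With 20% exposure in controls, an odds ratio of 1.5 implies 0.30 / 1.10 = 27.3% in cases. At 1:10 and two-sided 5%, a two-proportion approximation gives power of about 33% and 83%. The protocol asks for 415 cases for 90%. The period split would lower power further.

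**The case against.** **The study never set out to estimate risk in the labelled population.** Safety objective 2 asks for a comparison in users without contraindications, and apart from prior VTE the exclusions implement it. This stands, and it means the objective needs no change. The sentence in section 9.9 still claims more.

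**Severity and line of therapy are not ignored.** The section 9.3.4 covariates match the fracture and prior-drug limbs of the 9.3.2 definitions, though drug use over one year only. This also stands. The defect is that control is conditional, not that it is absent.

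**Stratified analyses may cover it.** Sections 9.7.1 and 9.7.3.2 mention strata by (contra) indications, which could be read to include the new indications. But 9.7.3.2 concerns incidence rates, section 8 speaks of contraindications only, and for relative risks 9.7.3.3 commits only to strata by period. Detail may be left to the analysis plan. The exclusions and the claim about them are fixed here.

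**A reader might infer that most compared patients, in both groups, are outside the label.** The documents do not establish that. The SR shares predate both DHPCs, are not stated to be limited to users without contraindications, and omit the fracture-risk and BP-contraindication limbs. No share is given for SR starters from June 2013, who are analysed separately and whom the label change should have moved towards eligibility. The condition on other drugs dates only from 2014. BP starters can meet the 9.3.2 proxies through an earlier drug or a precaution such as reflux, so a majority off label follows only from the literal wording.

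**Forcing BP precautions and Garvan risk into the model is debatable.** Predicting exposure alone does not make a variable a confounder, and no link to the outcomes is shown. Candidate status is as far as this can be pressed.

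**Conclusion.** The statement in section 9.9 is wrong on the protocol's own description of the label. The restriction removes contraindications (prior VTE only in part) and does nothing about severity, which is the confounder that section names. That conclusion needs no arithmetic.

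The size is known only roughly. Before the DHPCs, at most 47.9% or 13.0% of SR users, depending on the source, met both the fracture and second-line proxies. These ceilings assume that the published shares carry over to users without contraindications. They could rise under the wider 9.3.2 definitions by an amount the protocol does not give. From June 2013 the documents support no figure for the SR group. The point deserves action, but it does not invalidate the comparison set by the safety objective.

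**What to change.** 1. Reword the restriction item in section 9.9 to say that it removes SR contraindications only and does not address osteoporosis severity or line of therapy.
2. Reconcile prior VTE between the Abstract and 9.3.2, where it is a contraindication, and 9.2.5.3, where it is an exclusion for one outcome only.
3. Pre-specify a supplementary comparison restricted, in both groups, to patients who meet the 9.3.2 severe-osteoporosis definition at cohort entry, stratified by prior use of another osteoporosis drug. Draw the matched controls from the same restricted cohort and report it beside the main analysis. The condition that no other drug is possible cannot be imposed on a BP comparator, so this subset should not be described as fully on label.
4. Optionally, add Garvan risk and the Appendix 14.3.2 list of BP contraindications and precautions to 9.3.4 as candidate covariates.

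Cost: wording and one further analysis, using variables already defined for the effectiveness study. The subset will have fewer cases and lower precision. Garvan risk can be computed only where age and either bone density or weight are recorded, so the report should state for each database which part of the definition was available.
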